## 8.2.4. Follow-up/Early Withdrawal Visit

For participants who will participate in the OLE period, no follow-up visit will be performed. For details see Section 10.4.

All participants who discontinue the study before Week 12 are encouraged to complete the early withdrawal visit (Visit 7, Week 12/Early Withdrawal). The procedures to be completed during this visit are listed in the SoA. Participants who complete all study visits (including Visit 7) will have a follow-up telephone call with the investigator to review AEs and health status.

Participants who continued treatment to the end of the double-blind treatment period (Week 12) or have completed the study as per Section 7.2 will continue to collect information on the number of seizures they experience using the e-diary until 2 weeks after the last dose of study medication. Participants can start treatment with a new AED when required during the follow-up period.

## 8.3. Efficacy Assessments

#### 8.3.1. Seizure counta

The primary efficacy evaluation will be the time to baseline monthly seizure count. To assess this endpoint, the number and type of seizures during the baseline period and during the double-blind treatment period needs to be documented carefully.

The participant and/or caregiver will be provided access to an (electronic) diary to record seizures and intake of study intervention. The e-diary will be an app downloaded on the smartphone owned by the participant. Only if the participant and/or caregiver do not own a smartphone, a smartphone programmed for the study will be provided.

-

<sup>a This section has been amended by Amendment INT-1

Participants must be compliant with the recording of information in the e-diary throughout the study. Seizures that will be entered during baseline and throughout the study include focal aware seizures with and without motor signs, focal impaired awareness seizures and focal to bilateral tonic-clonic seizures. Myoclonic, or other generalized seizures will not be entered.

Optionally, when the systems are available for the study, during some days of the baseline and treatment period and in a limited number of study centers, wearable devices may be used for remote registration of seizures. This is an exploratory technique and when required, details will be described in an addendum to the protocol.

## 8.3.2. Secondary Evaluationsa

## 8.4. Safety Assessments

The collection of AEs and concomitant medications will start after the ICF has been signed and will continue until the final study visit. All safety assessments listed below will be performed as specified in the SoA.

Any clinically relevant changes occurring during the study must be recorded on the Adverse Event section of the eCRF.

Any clinically significant abnormalities persisting at the end of the study/early withdrawal will be followed by the investigator until resolution or until a clinically stable endpoint is reached.

The study will include the following evaluations of safety and tolerability according to the time points provided in the SoA.

#### 8.4.1. Physical Examination

The study investigator, or other authorized and appropriately qualified designee, will perform the physical and neurological examinations. On Visits 2 through 6, a brief neurological examination should be performed, including assessment of eye movements, gait, and other findings relevant to evaluation of AEs.

Body weight will be measured as per the SoA. Body weight will be measured using a calibrated scale. Participants will be weighed at approximately the same time of day on the same scale, wearing underwear and a gown and without shoes; they will be instructed to empty their bladders

-

<sup>a This section has been amended by Amendment INT-1

before being weighed. (Note: if disrobing for weighing is logistically impossible, the participant should be dressed as lightly as possible, with consistency from visit to visit).

## 8.4.2. Vital Signs

Blood pressure measurements will be assessed in supine positions with a completely automated device. Manual techniques will be used only if an automated device is not available.

Supine blood pressure measurements should be preceded by at least 5 minutes of rest in a quiet setting without distractions (e.g., television, cell phones).

In addition, oral or tympanic temperature will be measured.

Vital signs should be measured in nonfasting conditions whenever possible.

# 8.4.3. Electrocardiogram (ECG)a

At screening, a triplicate ECG recording is required, i.e., 3 individual ECG tracings should be obtained as closely as possible in succession, but no more than 2 minutes apart. The full set of triplicates should be completed in less than 4 minutes.

At the other visits indicated in the SoA, single twelve-lead ECGs, intended for safety monitoring, will be recorded supine (following 5 minutes rest) so that the different ECG intervals (RR, PR, QRS, QT) can be measured at multiple time points at screening and during the study (see SoA). The ECG will be recorded until 4 regular consecutive complexes are available in good readable quality.

Hot and cold drinks and food should be avoided 30 minutes before an ECG measurement whenever possible.

Clinically relevant abnormalities occurring during the study should be recorded in the Adverse Event section of the eCRF/eSource. During the collection of ECGs, participants should be in a quiet setting without distractions (e.g., television, cell phones). Participants should rest in a supine position for at least 5 minutes before ECG collection and should refrain from talking or moving arms or legs. If blood sampling or vital sign measurement is scheduled for the same time point as ECG recording, the procedures should be performed in the following order: ECG, vital signs, blood draw. Please note that fasting blood draw may precede the ECG and vital signs in this study.

# 8.4.4. Clinical Safety Laboratory Assessments

Blood samples for serum chemistry and hematology and a random urine sample for urinalysis will be collected as noted in Section 11.2, Clinical Laboratory Tests. A central laboratory will be used for testing. The investigator must review the laboratory results, document this review, and record any clinically relevant changes occurring during the study in the AE section of the eCRF.

<sup>a The section has been amended by Amendment INT-2

[figure not shown]
## 8.4.5. Suicidal Risk Monitoring

JNJ-40411813 is considered to be a CNS-active compound. The sponsor considers it important to monitor for such events before and during this clinical study.

# **Columbia Suicide Severity Rating Scale (C-SSRS)**

An interview to assess the risk of suicidal ideation and behavior will be conducted at screening, through the double-blind treatment period and at follow-up/early withdrawal. The C-SSRS is a low-burden measure of the spectrum of suicidal ideation and behavior that was developed in the National Institute of Mental Health Treatment of Adolescent Suicide Attempters Study to assess severity and track suicidal events through any treatment (Posner 2007). The C-SSRS is a clinical interview providing a summary of both ideation and behavior that can be administered during any evaluation or risk assessment to identify the occurrence and intensity of suicidal thoughts and suicidal behaviors. It can also be used during treatment to monitor for clinical worsening. See Section 11.9 for details.

## 8.5. Pharmacokineticsa

[figure not shown]

<sup>a This section has been amended by Amendment INT-1 and INT-3

Study visit	Study Day	JNJ-40411813 and metabolites Relative to in-clinic dose	Brivaracetam or Levetiracetam Relative to in-clinic dose*	CCI
2	1	• 2 hours after dosing	

predose

2 hours after dosing

	• predose
4	29	

predose

1 hour after dosing

	

predose

1 hour after dosing

	• predose
6	57	• predose	• predose	• predose
7***	85***	after dosing (combine with other blood collection when feasible)	At the same time as sample for JNJ-40411813	-

Table 4: Schedule of collection of 2-mL PK blood samples

\*If the subject is taking levetiracetam XR once daily in the evening, then one PK sample for levetiracetam will be collected on Visits 2 and 4 (at the same time as the postdose sample for JNJ-40411813) and Visit 6 (at the same time as the predose sample for JNJ-40411813)

brivaracetam, and ccl using validated, specific and sensitive liquid chromatography mass spectrometry/mass spectrometry (LC-MS/MS) methods. Some plasma samples will be analyzed to document the presence of JNJ-40411813 metabolites ccl and perhaps other metabolites, or may be used to determine protein binding using qualified research methods or validated methods. If deemed necessary, the concentrations of other co-administered AEDs may

also be measured. In addition, plasma PK samples may be stored for future analysis of protein

Plasma samples will be analyzed to determine concentrations of JNJ-40411813, levetiracetam or

The exact dates and times of blood sampling must be recorded in the laboratory requisition form. In addition, the exact dates and times of the last administration of drug (administered at home or at the clinic) prior to collection of each pharmacokinetic sample should be documented.

[figure not shown]
Data will be listed for all participants with available plasma concentrations per treatment and study day. All concentrations below the limit of quantification (LOQ) or missing data will be labeled as such in the concentration data listings. Concentrations below the LOQ will be treated as zero in the summary statistics.

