# 6.3. Measures to Minimize Bias: Randomization and Blindinga

#### **Procedures for Randomization**

Central randomization will be implemented in this study. Participants will be randomly assigned to one of two treatment groups based on computer-generated randomization schedules prepared before the study by, or under the supervision of the sponsor.

The randomization will be balanced by using randomly permuted blocks CCI

The IWRS will assign a unique treatment code, which will dictate the treatment assignment and matching study drug kits for the participant. The requestor must use his or her own user identification and personal identification number each time when contacting the IWRS and will then give the relevant participant details to uniquely identify the participant.

For programming of the IWRS-system, the following cohort numbers will be applied:

- Cohort 1: first cohort with **ECI** dose level (approximately 40 participants receiving JNJ-40411813 and approximately 20 receiving placebo)
- Cohort 2: second cohort with a dose level of (approximately 40 participants receiving JNJ-40411813 and approximately 10 receiving placebo)
- Cohort 3: third cohort with a higher dose if the efficacy of the higher dose used in Cohort 2 is still insufficient (approximately 40 JNJ/ approximately 10 placebo)

-

<sup>a This section has been amended by Amendment INT-1

• Cohort 4: this cohort includes both a lower dose and a higher dose. This cohort will randomize 100 subjects in a ratio 40:40:20 (high dose/low dose/placebo). This cohort may follow Cohort 2.

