# 9.3. PK and PK/PD analysesa

Data for all participants who receive a dose of JNJ-40411813 and have at least one measurement of plasma concentration, will be included in the PK analysis. Plasma concentrations of JNJ-40411813 and metabolites including CCI levetiracetam/ brivaracetam and will be listed for all participants who received this active medication.

Descriptive statistics will be calculated for the plasma concentrations of JNJ-40411813 and metabolites including CCI levetiracetam/ brivaracetam and CCI at each applicable

time point. Statistics include sample size (n), mean, standard deviation, coefficient of variation (CV), geometric mean, median, minimum, and maximum.

Population PK and/or PBPK analyses of JNJ-40411813 and levetiracetam/brivaracetam may be performed on the data of this study in combination with data pooled from other studies. An objective of these analyses is to investigate the potential effects of covariates, such as demographics and concomitant drugs, on the PK of JNJ-40411813. The results of the population analyses may be reported separately.

PK and PD relationship will be explored, if feasible. The results of population PK/PD analyses will also be reported separately.

\_

<sup>a This section has been amended by Amendment INT-1

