5.7. Other Analyses

5.7.1. Pharmacokinetics/Pharmacodynamic

PK analyses will be performed by the pharmacometrics group in clinical pharmacology on the PK analysis set (PKAS), defined as participants who have received at least 1 dose of JNJ-40411813 and have at least 1 valid blood sample drawn for PK analysis.

Descriptive statistics will be calculated for the plasma concentrations of JNJ-40411813 and concentrations of JNJ-40411813 metabolites including concentrations of JNJ-40411813 metabolites including applicable time point. If warranted and feasible, summary statistics will be provided for brivaracetam and additional column. Statistics include number of participants (N), number of observations (n), mean, standard deviation, coefficient of variation (CV), geometric mean, median, minimum, and maximum. PK data may also be displayed graphically, plotting boxplots of PK concentrations over time by treatment group.

Population PK analysis of JNJ-40411813 may be performed on the data of this study in combination with data pooled from other studies. An objective of these analyses is to investigate the potential effects of covariates, such as demographics and concomitant drugs, on the PK of JNJ-40411813. If conducted, the results of the population analyses will be reported separately from the clinical study report.

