6.2. Appendix 2 Changes to Protocol-Planned Analyses

There have been no changes to protocol-planned analyses.

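### A rule that sets every concentration below the LOQ to zero makes the listed geometric mean 0 or not computable wherever such a value occurs

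*Protocol*

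**What the plan says.** Protocol 8.5 gives two rules for concentrations below the limit of quantification. For listings: "All concentrations below the limit of quantification (LOQ) or missing data will be labeled as such in the concentration data listings". For summaries: "Concentrations below the LOQ will be treated as zero in the summary statistics". The second rule names no exception.

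Protocol 9.3 then sets out the summaries for each applicable time point: "Statistics include sample size (n), mean, standard deviation, coefficient of variation (CV), geometric mean, median, minimum, and maximum". The synopsis has the same list. SAP 5.7.1 keeps the geometric mean: "Statistics include number of participants (N), number of observations (n), mean, standard deviation, coefficient of variation (CV), geometric mean, median, minimum, and maximum". The SAP has no rule of its own for values below the LOQ; the term appears only in its abbreviation list. Its Appendix 2 states: "There have been no changes to protocol-planned analyses". The protocol's zero rule therefore stands.

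The PK analysis set in SAP 5.7.1 is "defined as participants who have received at least 1 dose of JNJ-40411813" with at least one valid PK sample. Protocol 6.3 plans about 40 participants on active drug in each of Cohorts 1 to 3; for Cohort 2 the wording is "approximately 40 participants receiving JNJ-40411813 and approximately 10 receiving placebo".

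**The concern.** The geometric mean is the one statistic on the list that cannot absorb a zero. If the zero rule is applied as written, a single value below the LOQ replaces the geometric mean of a whole time point with 0 or with a blank. If it is not applied, someone has to choose another treatment during programming, and the plan does not say which. The candidate treatments give visibly different numbers. One of them, leaving the zeros out, also puts the geometric mean on a smaller n than the arithmetic mean printed beside it.

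At stake is a descriptive statistic that serves a secondary objective, the pharmacokinetics of JNJ-40411813, selected metabolites and levetiracetam or brivaracetam. No test, threshold or efficacy result depends on it.

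**Working it through.** The plan gives no figure to reproduce on this point, so the check is of the definition, followed by an illustration.

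**1. Definition.** GM = (x₁ × … × xₙ)^(1/n) = exp[(1/n) Σ ln xᵢ]. If any xᵢ = 0, the product is 0 and so is its root; in the log form ln 0 does not exist. The arithmetic mean, SD, median, minimum and maximum accept zeros. So does the CV, provided at least one value is quantifiable, so that the mean is not zero.

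**2. Hand example (assumed values).** Take 39 values of 500 ng/mL and one below the LOQ.
- Arithmetic mean with zero: (39 × 500 + 0)/40 = 487.5.
- GM with zero: 0, or not computable.
- GM with the value left out: 500 on n = 39.
- GM with LLOQ/2: 500 × [(LLOQ/2)/500]^(1/40). This is 500 × 0.001^(0.025) ≈ 421 for an assumed LLOQ of 1 ng/mL, and 500 × 0.005^(0.025) ≈ 438 for 5 ng/mL.

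**3. Example with spread.** The input n = 40 is the planned active group per cohort. The rest is assumed: evenly spaced quantiles of a lognormal distribution, median 500 ng/mL, CV 50%, LOQ 1 or 5 ng/mL. The lowest values are replaced.

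| Values below LOQ | Arithmetic mean, zeros in | Median, zeros in | GM, zeros in | GM, zeros left out | GM, LOQ/2 (LOQ 1 / 5) |
|---|---|---|---|---|---|
| 0 | 556.7 | 500.1 | 500.0 | – | – |
| 1 | 552.4 | 500.1 | 0 | 513.8 (n = 39) | 432.0 / 449.7 |
| 4 | 534.4 | 500.1 | 0 | 547.5 (n = 36) | 271.9 / 319.4 |

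With one such value, leaving it out moves the geometric mean by +2.8% (513.8/500.0). LOQ/2 moves it by −13.6% or −10.1%, depending on the LOQ.

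**4. How often.** The documents give no rate. For an assumed independent per-sample rate p, the chance of at least one value below the LOQ among 40 is 1 − (1 − p)^40: 33% at p = 1%, 55% at 2%, 87% at 5% and 98.5% at 10%. These are a range of assumptions, not estimates.

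**5. Where.** Table 4 schedules no JNJ-40411813 predose sample on Day 1, and participants who only ever received placebo are outside the PK set, so neither source forces zeros for the parent drug. Metabolites are more exposed: they are sampled 2 hours after the first dose, and Protocol 8.5 treats the presence of some metabolites as something still to be documented.

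**The case against.** The best defence is that the failure is conditional and small. It needs a value below the LOQ, and no rate is given. The tables are descriptive; the arithmetic mean, median and minimum stand next to the geometric mean, so a zero shows as a minimum of 0; and the listings flag each such value. All of this stands. It limits the weight of the point but does not supply the missing convention.

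Several stronger readings are tempting, and the documents do not support them.

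- *A reader might infer that the two rules contradict each other.* They do not, strictly: a geometric mean reported as 0 or as not calculable obeys both. The result is uninformative rather than impossible.
- *A reader might infer that the geometric mean fails wherever someone missed doses.* For the parent drug, Protocol 2.2.2 gives single-dose mean terminal half-lives of 10.6 to about 27 hours, and SAP 1.2 gives twice-daily dosing. Twelve extra hours leave 2^(−12/10.6) ≈ 46% to 2^(−12/27) ≈ 73% of the trough. A 100-fold fall takes log₂100 ≈ 6.6 half-lives, which is about 3 to 7.5 days off drug. Enzyme inducers could shorten this, but one missed dose is unlikely to be enough.
- *A reader might infer that one particular metabolite will be mostly below the LOQ.* Protocol 2.2.1 describes a rat metabolite not found in human plasma, but the names of the measured metabolites are redacted, so the link cannot be made.
- *A reader might infer that the zero rule is expressly carried into the open-label extension.* Protocol 10.8.5 points to 8.5 for assay procedures only, and 10.9.3 points to 9.3, which has no rule for values below the LOQ.
- *A reader might infer that the reported value will be biased upward because software drops zeros.* The documents do not say how zeros will be programmed.

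**Conclusion.** The point holds, as a minor one. By a rule that the plan states, any analyte and time point with at least one value below the LOQ gets a geometric mean of 0 or none at all. No other section exempts this statistic or substitutes another value. The arithmetic conclusion rests on the definition alone. The size of the alternatives (513.8 with the value left out, 432.0 or 449.7 with LOQ/2, against 500.0) rests on assumed concentrations and LOQs. The frequency is unknown: it could be nil for the parent drug and is most plausible for metabolites. Only the descriptive PK tables are affected; the efficacy and safety analyses are not.

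**What to change.** In Protocol 8.5 and SAP 5.7.1:

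- Limit the zero rule to the arithmetic mean, SD, CV, median, minimum and maximum.
- Exempt the geometric mean and prespecify one convention for it. It could be computed on quantifiable values with its own n, or not reported when values are below the LOQ. LLOQ/2 is another option, but the result then depends on the LLOQ, as the working shows. The choice matters less than fixing it in advance.
- Show the number of values below the LOQ for each analyte at each time point.
- Say whether the same rule applies to the open-label extension.

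The cost is about one sentence in each document and one extra row in the PK tables. No data collection changes.

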#### 8.6. Genetics

Status: Approved, Date: 17 November 2022

binding, biomarkers and the metabolite profile

## 8.7. Biomarkers

During the study, blood will be collected for the assessment of the biomarkers CCI time points indicated in the SoA (see also Section 4.2.) Additional instructions for collection of biomarker samples:

- Blood biomarkers will be collected under fasting conditions at least 4 hours, water permitted with the exception of the postdose collection during Visit 2.
- Participants should be informed not to do strenuous sports or exercises within 24 hours before blood sample collection.

Biomarkers may be added or deleted based on scientific information or technical innovations under the condition that the total volume of blood collected will not be increased.

#### Participant data

To evaluate the biomarker results, the following information needs to be documented on each day of collection of blood samples for biomarker analysis.

- Diet (extremes during the previous week)
- Any sickness or allergy in the previous 2 weeks

#### 8.8. Adverse Events and Serious Adverse Events

Timely, accurate, and complete reporting and analysis of safety information from clinical studies are crucial for the protection of participants, investigators, and the sponsor, and are mandated by regulatory agencies worldwide. The sponsor has established Standard Operating Procedures in conformity with regulatory requirements worldwide to ensure appropriate reporting of safety information; all clinical studies conducted by the sponsor or its affiliates will be conducted in accordance with those procedures.

AEs will be reported by the participant (or, when appropriate, by a caregiver, surrogate, or the participant's legally acceptable representative) for the duration of the study.

As with any CNS-active medication, investigators should monitor carefully and document any CNS-related AE including tremor, ataxia, abnormal sensation, confusion, or possibility of seizure.

For further details on AEs and SAEs (Definitions and Classifications; Attribution Definitions; Severity Criteria; Special Reporting Situations; Procedures) as well as product quality complaints

(PQCs), refer to Section 11.4, Adverse Events: Definitions and Procedures for Recording, Evaluating, Follow-Up, and Reporting.

